## 10.9. Appendix 9: Child-Pugh Classification (CPC) of Liver Dysfunction

**Table 5. Scoring for Child-Pugh Classification**

Cohort	CPC	Level of dysfunction	Total Score (tally based on assessment of parameters in Table 6)
1	Not Applicable	Without hepatic impairment	Not Applicable
NA	A	Mild	5-6
2	B	Moderate	7-9
NA	C	Severe	≥10

**Table 6. Derivation of Child-Pugh Classification Score**

Assessment Parameters	Assigned score for observed findings		
	1 point	2 points	3 points
Encephalopathy grade a (refer to Table 7 below)	0	1 or 2	3 or 4 a
Ascites	Absent	Asymptomatic	Requiring intervention
Serum total bilirubin, mg/dL	<2	2 to 3	>3
Serum albumin, g/dL	>3.5	2.8 to 3.5	<2.8
Prothrombin time, sec prolonged b	<4	4 to 6	>6

a. Participants with a prior history of Grade 3 or Grade 4 encephalopathy who are *currently* receiving an intervention [for example: lactulose or lactitol, alone or in combination with rifaximin, and/or neomycin] to manage encephalopathy-related signs and symptoms should be scored for encephalopathy grading *based on their presentation while on intervention at the Screening visit* and can be included in this study as long as they do *not* have clinically active Grade 3 or Grade 4 encephalopathy.

b. As assessed relative to PT control (*or* upper limit of normal).

**Table 7. Determination of Encephalopathy Grade**

Encephalopathy Grade	Definition
0	Normal consciousness, personality, neurological exam
1	Restless, sleep disturbed, irritable/agitated, tremor, impaired handwriting
2	Lethargic, time disoriented, inappropriate, asterixis, ataxia
3 a	Somnolent, stuporous, place disoriented, hyperactive reflexes, rigidity
4 a	Unrousable coma, no personality/behavior, decerebrate

a. Participants with clinically active Grade 3 or 4 encephalopathy are excluded.

**CPC should be assessed *at Screening* to determine the classification of a given participant.**

## 10.10. Appendix 10: Abbreviations

The following is a list of abbreviations that may be used in the protocol.

Abbreviation	Term
→	ongoing/continuous event
3CL pro	3C-like protein
Ab	antibody
Abs	absolute
ADL	activities of daily living
CCI	[REDACTED]
AE	adverse event
CCI	[REDACTED]
CCI	[REDACTED]
ALT	alanine aminotransferase
ANOVA	analysis of variance
aPTT	activated partial thromboplastin time
AST	aspartate aminotransferase
AUC	area under the curve
CCI	[REDACTED]
CCI	[REDACTED]
AUC inf	area under the plasma concentration-time profile from time 0 extrapolated to infinite time
AUC last	area under the plasma concentration-time profile from time 0 to the time of C last
AV	atrioventricular
β-hCG	beta-human chorionic gonadotropin
BBS	Biospecimen Banking System
BID	twice a day
BMI	body mass index
BP	blood pressure
bpm	beats per minute
BUN	blood urea nitrogen
CFR	Code of Federal Regulations
CI	confidence interval
CIOMS	Council for International Organizations of Medical Sciences
CK	creatinine kinase
CKD	chronic kidney disease
CKD-EPI	Chronic Kidney Disease-Epidemiology Collaboration
CCI	[REDACTED]
C last	predicted plasma concentration at the last quantifiable time point

Abbreviation	Term
CCI	[REDACTED]
C max	maximum plasma concentration
CO 2	carbon dioxide (bicarbonate)
COVID-19	coronavirus disease 2019
CPC	Child-Pugh score
CRF	case report form
CRO	contract research organization
CRU	clinical research unit
CSR	Clinical Study Report
CT	clinical trial
CYP	cytochrome P450
CYP3A4	cytochrome P450 3A4
DBP	diastolic blood pressure
DC	discontinuation
DCT	data collection tool
DDI	drug-drug interaction
DILI	drug-induced liver injury
DMC	Data Monitoring Committee
DNA	deoxyribonucleic acid
EC	ethics committee
ECC	Emergency Contact Card
ECG	electrocardiogram
eCRF	electronic case report form
EDB	exposure during breastfeeding
EDP	exposure during pregnancy
eGFR	estimated glomerular filtration rate
EMA	European Medicines Agency
EU	European Union
EudraCT	European Clinical Trials Database
FDA	Food and Drug Administration
FIH	first-in-human
f m	fraction metabolized
FSH	follicle stimulating hormone
f u	fraction unbound
GCP	Good Clinical Practice
GGT	gamma-glutamyl transferase
GLP	Good Laboratory Practice
H	hour
HBcAb	hepatitis B core antibody
HBsAb	hepatitis B surface antibody
HBsAg	hepatitis B surface antigen
HCoV-OC43	human coronavirus OC43
HCoV-229E	human coronavirus 229E

Abbreviation	Term
HCoV-HKU1	human coronavirus HKU1
HCoV-NL63	human coronavirus NL63
HCVAb	hepatitis C antibody
HCV	hepatitis C virus
hep C	hepatitis C
HI	hepatic impairment
HIV	human immunodeficiency virus
HMG CoA reductase	3-hydroxy-3-methyl-glutaryl-CoA reductase
HR	heart rate
HRT	hormone replacement therapy
IB	Investigator's Brochure
ICD	informed consent document
ICH	International Council for Harmonisation
IMP	investigational medicinal product
IND	Investigational New Drug
INR	international normalized ratio
IP	investigational product
IP manual	investigational product manual
IPAL	Investigational Product Accountability Log
IRB	Institutional Review Board
IV	intravenous
$k_{el}$	elimination rate constant
$K_i$	inhibition constant
LFT	liver function test
MAD	multiple ascending dose
MCH	mean corpuscular hemoglobin
MCHC	mean corpuscular hemoglobin concentration
MCV	mean corpuscular volume
MERS	Middle East respiratory syndrome
MRI	magnetic resonance imaging
N/A	not applicable
NHP	non-human primate
NNRT	non-nucleoside reverse transcriptase
NOAEL	no observed adverse effect level
NTI	narrow therapeutic index
PAH	pulmonary arterial hypertension
PBPK	physiologically based pharmacokinetic
PD	pharmacodynamic(s)
PE	physical examination
pH	potential of hydrogen
PI	principle investigator
PK	pharmacokinetic(s)
PR	pulse rate

Abbreviation	Term
PT	prothrombin time
PT-INR	prothrombin time-international normalized ratio
PVC	premature ventricular contraction/complex
q12h	every 12 hours
QT	time from the beginning of the QRS complex to the end of the T wave
QTc	corrected QT interval
QTcF	corrected QT (Fridericia method)
qual	qualitative
RBC	red blood cell
RNA	ribonucleic acid
RT-PCR	reverse-transcriptase polymerase chain reaction
SAD	single ascending dose
SAE	serious adverse event
SAP	Statistical Analysis Plan
SARS-CoV-1	severe acute respiratory syndrome coronavirus 1
SARS-CoV-2	severe acute respiratory syndrome coronavirus 2
SBP	systolic blood pressure
SoA	schedule of activities
SOP	standard operating procedure
SRSD	single-reference safety document
SToD	Study Team on Demand
SUSAR	suspected unexpected serious adverse reaction
T4	thyroxine
TBili	total bilirubin
TEAE	treatment emergent adverse event
THC	tetrahydrocannabinol
TIPS	transjugular intrahepatic portosystemic shunt
CCI	
TSH	thyroid stimulating hormone
ULN	upper limit of normal
US	United States
USPI	United States Prescribing Information
CCI	
WBC	white blood cell
WHO	World Health Organization
WOCBP	woman/women of childbearing potential

1. AMENDMENTS FROM PREVIOUS VERSION(S)

None.

2. INTRODUCTION

PF-07321332/ritonavir is intended for short-term (eg, 5 day) use, in patients with COVID-19, some of whom may have some degree of impaired hepatic function. The purpose of this study is to estimate the effect of hepatic impairment on the plasma PK of PF-07321332/ritonavir. Findings from this study will be used to develop dosing recommendations so that the dose and/or dosing interval may be adjusted appropriately in the presence of hepatic impairment.

2.1. Study Design

This is a Phase 1, non-randomized, open-label study to investigate the effect of hepatic impairment on the plasma PK, safety and tolerability of a single oral dose of PF-07321332 in combination with the PK boosting agent ritonavir in approximately 16 participants. The study will be conducted in adult participants with stable, moderate hepatic impairment and a control group of participants with normal hepatic function.

Enrollment will be in a staged manner such that participants with hepatic impairment (Cohort 2) will begin enrollment first. Participants without hepatic impairment (Cohort 1) will begin recruitment towards the end of Cohort 2 or earlier, at the sponsor's discretion such that the enrollment in both cohorts may overlap. Participants in Cohort 1 will match the average demographics (at a minimum, age and weight; gender and race as much as practically possible) of participants in Cohort 2.

All participants in both cohorts will provide informed consent and undergo Screening evaluations to determine their eligibility. Categorization of participants into hepatic impairment cohort, Cohort 2, will be done based on Child-Pugh scores.

Participants who prematurely discontinue for non-safety related reasons may be replaced, at the discretion of the PI and sponsor study team.

Each enrolled participant will receive a single 100 mg dose of PF-07321332 administered orally in combination with the PK boosting agent ritonavir administered as a 100 mg dose at -12, 0, 12, and 24 hours relative to PF-07321332 dosing.

The total planned duration of participation, from the Screening visit to the last Follow-up phone call, is approximately up to 9 weeks.

Table 1. Hepatic Function Categories Based on Child-Pugh Score

Cohort	Description	Child-Pugh Score	Number of Participants
1	Without hepatic impairment	Not Applicable	8
2	Moderate hepatic impairment	Class B (7 to 9 points)	8

2.2. Study Objectives

[figure not shown]
2.2.1. Primary Objective

- *To compare the PK of PF-07321332, following a single oral dose administration of PF-07321332 pharmacokinetically boosted with ritonavir in adult participants with moderate hepatic impairment and age and body weight-matched participants without hepatic impairment.*

2.2.2. Secondary Objective

- *To evaluate the safety and tolerability of PF-07321332 and ritonavir, following a single oral dose administration of PF-07321332 pharmacokinetically boosted with ritonavir, in participants with moderate hepatic impairment and in healthy participants with normal hepatic function.*

CCI

3. INTERIM ANALYSES, FINAL ANALYSES AND UNBLINDING

No formal interim analysis will be conducted for this study. As this is an open-label study, the sponsor may conduct unblinded reviews of the data during the course of the study for the purpose of safety assessment, facilitating PK/PD modeling, and/or supporting clinical development.

Final analysis will follow the official database release. As this will be an open-label study, there is no formal unblinding of the randomization code.

4. HYPOTHESES AND DECISION RULES

4.1. Statistical Hypotheses

No hypotheses are required.

4.2. Statistical Decision Rules

No decision rules are required.

5. ANALYSIS SETS

5.1. Enrolled Set

"Enrolled" means a participant's, or his or her legally authorized representative's, agreement to participate in a clinical study following completion of the informed consent process and screening. A participant will be considered enrolled if the informed consent is not withdrawn prior to participating in any study activity after screening. Potential participants who are screened for the purpose of determining eligibility for the study, but do not participate in the study, are not considered enrolled, unless otherwise specified by the protocol.

5.2. Pharmacokinetic (PK) Analysis Set

5.2.1. Concentration Analysis Set

The PK concentration population is defined as all participants assigned to investigational product and treated who have at least 1 concentration measured.

5.2.2. Parameter Analysis Set

The PK parameter analysis population is defined as all participants assigned to investigational product and treated who have at least 1 of the PK parameters of primary interest measured.

5.3. Pharmacodynamic Analysis Set

None.

5.4. Safety Analysis Set

All participants randomly assigned to study intervention and who take at least 1 dose of study intervention. Participants will be analyzed according to the product they actually received.

5.5. Other Analysis Sets

None.

5.6. Treatment Misallocations

All analyses will be performed on an "as-treated" basis and will not include data from subjects who are randomized but not treated.

5.7. Protocol Deviations

Subjects who experience events that may affect their PK profile (eg lack of compliance with dosing) may be excluded from the PK analysis. At the discretion of the pharmacokineticist a concentration value may also be excluded if the deviation in sampling time is of sufficient concern or if the concentration is anomalous for any other reason.

A full list of protocol deviations will be compiled and reviewed to identify major and minor deviations prior to database closure.

5.7.1. Deviations Assessed Prior to Randomization

At Screening, the investigator will assess subjects against the inclusion and exclusion criteria as set out in Sections 5.1 and 5.2 of the protocol.

5.7.2. Deviations Assessed Post-Randomization

A full list of protocol deviations for the study report will be compiled prior to database closure. Any significant deviation from the protocol will be reviewed prior to database closure and a decision taken regarding evaluation for each analysis population.

6. ENDPOINTS AND COVARIATES

6.1. Efficacy Endpoint(s)

None.

6.2. Safety Endpoints

Any events occurring following start of treatment (of PF-07321332) or increasing in severity will be counted as treatment emergent.

Events that occur in a non-treatment period (for example, Follow-up) will be counted as treatment emergent and attributed to the previous treatment taken.

The following data are considered in standard safety summaries (see protocol for collection days and list of parameters):

- *adverse events*,
- *laboratory data*.

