- b. Contact may occur via telephone contact and must occur 28 to 35 days from administration of PF-07321332 or from the time of early termination/discontinuation.
- c. Demographics will include race, age, and gender.
- d. Complete physical examination will be performed at screening; and limited PE will be conducted on Day -1, Day 3, early termination, and at any time point as deemed necessary by the investigator.
- e. Safety laboratory assessments include chemistry, hematology, and urinalysis (and microscopy, if needed) and must be collected following at least a 4 hour fast.
- f. The Child-Pugh classification ([Appendix 9](#)) will be used to define the participants of Cohort 2 with moderate hepatic impairment (Child-Pugh Class B) at Screening.
- g. Confirmation of the correct use of appropriate contraceptive method.
- h. Single 12-lead ECG readings will be taken pre-dose on Day 1 and at specified times. All ECG assessments will be made prior to any blood draws or vital sign measurements.
- i. Single seated BP and PR will be performed pre-dose on Day 1 and at specified times. All BP and PR will be measured prior to collection of blood draws if scheduled at the same time, after collection of ECGs.
- j. Testing will be performed as described in [Appendix 2](#).

PFIZER CONFIDENTIAL

Visit Identifier a	Screening	Day -1	Day 1	Day 2	Day 3	Early Termination/ DC	Follow-up Contact
Days Relative to Day 1 Abbreviations used in this table can be found in Appendix 10	Day -28 to Day -2						28-35 Daysb

k. Ritonavir will be administered on Day -1 at -12 hours, Day 1 at 0 hours and 12 hours, and Day 2 at 24 hours, relative to PF-07321332 dosing.  
l. Blood samples are to be collected for plasma PK assessment of PF-07321332 CCI [REDACTED] on Day 1 at 0 (pre-dose for PF-07321332), 0.5, 1, 2, 3, 4, 6, 8, 10, and 12 hours, Day 2 at 24 and 36 hours, and Day 3 at 48 hours, relative to PF-07321332 dosing, and at early termination/DC (if before 48 hours post-dose for PF-07321332), if needed.

CCI [REDACTED]  
[REDACTED]

o. Testing for COVID-19 pathogen will be performed prior to being admitted to the clinic for confinement, on Day -1, and if participant develops COVID-19 like symptoms.  
p. To be done at least daily during residence.  
q. Check exposure to positive case, residence or travel in area of high incidence and COVID-19 related signs and symptoms.  

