## 3. OBJECTIVES AND ENDPOINTS

Objectives	Endpoints
Primary:	Primary:

To compare the PK of PF-07321332, following a single oral dose administration of PF-07321332 pharmacokinetically boosted with ritonavir in adult participants with moderate hepatic impairment and age and body weight-matched participants without hepatic impairment.

	

Plasma PF-07321332 PK parameters: <math>C_{max}</math>, <math>AUC_{last}</math>, <math>AUC_{inf}</math>(if data permit)

Secondary:	Secondary:

To evaluate the safety and tolerability of PF-07321332 and ritonavir, following a single oral dose administration of PF-07321332 pharmacokinetically boosted with ritonavir, in participants with moderate hepatic impairment and in healthy participants with normal hepatic function.

	

Incidence of TEAEs, abnormal ECGs, vital signs, and laboratory values

CC1 	

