### **6. STUDY INTERVENTION(S) AND CONCOMITANT THERAPY**

Study intervention is defined as any investigational intervention(s), marketed product(s), placebo, medical device(s), or study procedure(s) intended to be administered to a study participant according to the study protocol.

For the purposes of this protocol, study intervention refers to PF-07321332 and ritonavir.

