#### **6.1. Study Intervention(s) Administered**

For this study, the investigational products are PF-07321332 (provided as 100 mg tablets) and ritonavir (provided as 100 mg tablets).

PF-07321332 100 mg tablets and ritonavir 100 mg tablets will be supplied by Pfizer to the CRU in bulk along with individual dosing containers for unit dosing.

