8.3. Safety Analysis

A set of summary tables split by hepatic function group will be produced to evaluate any potential risk associated with the safety and toleration of administering PF-07321332.

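### SAP 6.2 starts treatment emergence at the PF-07321332 dose, 12 hours after the first dose of study intervention, so new events in that window miss TEAE incidence unless they later worsen

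*SAP*

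**What the plan says.** SAP 6.2 defines emergence in two sentences. The first is "Any events occurring following start of treatment (of PF-07321332) or increasing in severity will be counted as treatment emergent". The second is "Events that occur in a non-treatment period (for example, Follow-up) will be counted as treatment emergent and attributed to the previous treatment taken". The protocol only expands the abbreviation TEAE.

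Other sections treat ritonavir as part of what is being studied:

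- Protocol 6: "For the purposes of this protocol, study intervention refers to PF-07321332 and ritonavir".
- Protocol 6.1: "the investigational products are PF-07321332 (provided as 100 mg tablets) and ritonavir (provided as 100 mg tablets").
- Protocol 3, secondary objective: "To evaluate the safety and tolerability of PF-07321332 and ritonavir, following a single oral dose administration of PF-07321332 pharmacokinetically boosted with ritonavir". TEAE incidence is among its endpoints.
- SAP 2.1 gives the schedule: "ritonavir administered as a 100 mg dose at -12, 0, 12, and 24 hours relative to PF-07321332 dosing". Footnote k of the Schedule of Activities (Protocol 1.3) puts the first of these doses on Day -1.
- SAP 5.4 and Protocol 9.2 set the dosing condition for the safety set at one or more doses of study intervention.
- Protocol 8.3.1 collects adverse events from consent to at least 28 days after the last dose of study intervention.

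SAP 8.3, by contrast, describes the safety tables as meant "to evaluate any potential risk associated with the safety and toleration of administering PF-07321332", without naming ritonavir. SAP 8.3.4 leaves the layout of adverse event reporting to sponsor standards that are not in the documents.

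**The concern.** The numerator and denominator of TEAE incidence start at different exposures. A participant can enter the safety set on the Day -1 ritonavir dose, but the numerator opens only with PF-07321332, 12 hours later. An event caused by the first ritonavir dose would then be missing from the secondary endpoint meant to describe the safety of both drugs.

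The same sentence has a second weakness. Its limb on worsening severity has no starting point, while events are collected from consent. Read literally, an event that worsened during screening, before any dose, would count as treatment emergent.

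**Working it through.** The plan states no figure that depends on this definition, so there is none to reproduce. The check is to apply the definition to cases and then size the window.

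**Applying SAP 6.2 as written**

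| Case | After PF-07321332? | Worsens? | TEAE? |
|---|---|---|---|
| New event at -6 h, resolves | No | No | No |
| New event at -6 h, worsens after 0 h | No | Yes | Yes |
| Event worsens in screening, before any dose | No | Yes | Yes, read literally |
| Takes only Day -1 ritonavir, has an event that does not worsen, stops | Never dosed | No | No |

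In the first and last cases the participant meets the dosing condition for the safety set. In the last case, if the event is why dosing stopped, SAP 8.3.3 would count a discontinuation due to an adverse event with no matching TEAE. This is possible under the plan, because Protocol 7.1 lists adverse events among the reasons to stop study intervention.

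**Does the second sentence of SAP 6.2 rescue the first case?** Not clearly. Its only example is Follow-up, and it attributes the event to a treatment already taken. The interval from -12 h to 0 h comes before treatment as the first sentence defines it, and follows a dose of investigational product. If the sentence is stretched to cover that interval, the two sentences of SAP 6.2 classify the same event differently.

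**Where other sections start the clock.** Protocol 6.8 classes treatments as concomitant from the first dose of study intervention. A drug given for an event at -6 h is therefore concomitant, while the event is not treatment emergent. Day -1 safety assessments are done before dosing (Protocol 1.1 and 4.1), and the only Day -1 dose is ritonavir, so the laboratory baseline (SAP 8.3.5) precedes ritonavir. Adverse events and laboratory data are the two standard safety summaries named in SAP 6.2, and they start at different points.

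**Size of the window**

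Inputs: ritonavir at -12, 0, 12 and 24 h; PF-07321332 at 0 h; collection to at least 28 days after the last dose; follow-up contact 28 to 35 days after PF-07321332; 8 participants per cohort.

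- Gap: 0 - (-12) = 12 h, following 1 of 4 ritonavir doses.
- Collection from first dose to 28 days after the last ritonavir dose: (12 + 24) + 28 × 24 = 36 + 672 = 708 h. Share: 12/708 = 1.7%.
- To a contact 28 days after PF-07321332: 12 + 672 = 684 h. Share: 12/684 = 1.8%.
- To a contact 35 days after PF-07321332: 12 + 840 = 852 h. Share: 12/852 = 1.4%.
- From first dose to the 48 h PK sample: 12/(12 + 48) = 12/60 = 20%.
- One participant whose only event is in the window: 1/8 = 12.5 points in the cohort, 1/16 = 6.25 points overall.

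**How often it might matter.** The documents give no event rate for the window. Suppose each participant independently has probability p of a new, non-worsening event there. The chance of at least one such participant is 1 - (1 - p)^n:

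| Assumed p | n = 8 | n = 16 |
|---|---|---|
| 2% | 14.9% | 27.6% |
| 5% | 33.7% | 56.0% |
| 10% | 57.0% | 81.5% |
| 20% | 83.2% | 97.2% |

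These values of p are assumptions chosen to show a range.

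**The case against.** The strongest reply is that the anchor is deliberate. SAP 6.2 names the drug in parentheses. Study days and the follow-up contact are counted from PF-07321332, SAP 8.3 aims the safety tables at that drug, and Protocol 2.2 describes ritonavir purely as a booster. The secondary objective speaks of safety following the PF-07321332 dose, which can be read as fixing the period. In addition, ECG and vital-sign baselines are taken before dosing on Day 1, about 12 hours after the first ritonavir dose, so moving only the adverse event anchor would separate components of one endpoint.

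Part of this stands. The choice may be intended, and the objective's wording allows that reading. It still leaves an objective that names ritonavir without TEAE coverage of the first ritonavir dose, and a safety set that can be entered on that dose. The baseline argument is weaker, because SAP 8.3.6 and 8.3.7 say only that vital signs and ECGs will be databased and available on request, whereas the laboratory summary already starts before ritonavir.

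The reply is also right that little safety information is lost. Events stay on the CRF, SAEs are reported within 24 hours, causality is assessed for every event, and the rule is the same in both cohorts. The 12.5 points is just 1/8 and would apply to any single event. That supports a minor rating but does not repair the definition.

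**Conclusion.** The definition is wrong as written, and the consequence is minor. On the plain reading of SAP 6.2, new events in the 12 hours after the first ritonavir dose are left out of a stated secondary endpoint unless they later worsen, and the numerator starts after the exposure that can put a participant in the denominator.

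The mismatch follows from the text alone. Its practical effect depends on whether any such event occurs, which the documents do not let us estimate, and on the sponsor standards, which may or may not show these events in an all-event table or listing. Safety is summarised descriptively, with no hypotheses or decision rules, and the PK comparison does not use this definition.

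**What to change.** In SAP 6.2, define an event as treatment emergent if its onset, or an increase in its severity, comes after the first dose of any study intervention, which is the Day -1 ritonavir dose. This also gives the worsening limb a starting point. Add a flag that places each event in the ritonavir-only period or after PF-07321332, so that the count anchored on PF-07321332 can still be shown.

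If the present anchor is intended, state that in SAP 6.2, start the worsening limb there too, and report ritonavir-only events separately.

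The cost is one sentence and one derivation flag on data already collected, with no new assessments. Under the first option, new-onset TEAE counts cannot fall. An event that worsened only before the first dose, which counts under the literal current text, would drop out.
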